Health care claims data were provided at the individual employee level by Cigna and were used to calculate spending and utilization variables. These administrative data are available for all worksites (treatment, primary control, and secondary controls), but only for the roughly 37% of employees who were enrolled in a BJ's employer-sponsored Cigna health insurance plan at any given time. Full time workers were more likely to have Cigna coverage than part-time workers. We analyzed medical claims for BJ's employees (but not their dependents, who were not directly exposed to the treatment).

We aggregated medical spending and utilization at the employee level across our 36-month treatment period. To standardize utilization outcome variables across employees who may have been employed and in our sample for different lengths of time, we normalized outcomes for partial-year enrollees to annual values. For each employee, we exclude any claims with service dates prior to either the employee's hire date or the start of Cigna eligibility status as well as any claims with service dates more than 30 days after the employee's termination or end of Cigna enrollment.

We examined the following outcomes at the individual level as well as the worksite level. In worksite-level analyses, results are shown per 2000 work hours for all the continuous outcomes to normalize across sites of different sizes. An exception was the number of distinct medications, which we constructed at the worksite level using a weighted average of individual values based on hours worked at the worksite.

- **Total medical spending:** We defined total medical spending per year as the sum of all payments made for health care – deductibles, copayments, coinsurance, insurance payments, and “amount paid by other carrier” – that appear on an employee's claims.
- **Medical utilization:** We defined three medical utilization variables (i.e. counts of services provided):
 - *Office Visits:* We defined an office visit as a claim line with site of care as “office” or “on-campus outpatient hospitals” and service type as “physician visit.” We counted as one office visit such an occurrence at the level of a unique combination of patient, service date, and provider specialty. In other words, if an office code appears on multiple claim lines on the same date and billed by the same provider specialty, we counted these as a single visit. We do not include office visits that occurred with the site of care as

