We designed our analyses based on two study samples. Our main study sample comprised all employees who worked for any duration of time at BJ’s Wholesale Club during the study period. In other words, we included any worker who worked at BJ’s for any length of time during the study period. This is the most inclusive sample.

A potential drawback of these sample inclusion criteria is the possibility of endogenous entry or exit based on the treatment itself. For example, a worker’s decision to join or leave employment at BJ’s Wholesale Club could be a function of the availability of, or exposure to, the wellness program. Therefore, we also defined a relatively stable subsample of employees who were continuously employed at BJ’s in the months before the treatment. This “stably employed” subsample comprised all employees working at BJ’s during, at minimum, the 13 consecutive weeks immediately prior to the onset of the treatment—and thus cannot have entered because of the treatment. Exit from this sample might still be endogenous in theory, however. We will therefore gauge the potential bias introduced by any observed differences in exit between treatment and control sites using a bounding exercise. Additional details on the construction of this subsample are provided below and in the appendix.

B. Balance between treatment and control

We tested balance between treatment and control groups on observable baseline characteristics. We examined balance on demographic variables (age, sex, and race) for all of the analytical samples. We also examined balance on job and employment characteristics in the pre-intervention period for the stably employed subsample, as they by construction were in jobs with characteristics defined prior to the intervention and thus exogenous to the treatment status.

As **Table 8** demonstrates at the employee level, our randomly assigned worksites were balanced on many employee characteristics, but not all. Notably, while treatment and control site workers

⁸ This indicator was our primary definition of participation in our prior phase 1 analysis. Given that we expanded the sample size for phase 2 (with a different total number of modules available), we believe the continuous measure is preferable here.

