were similar on age and gender, a greater proportion of treatment site workers were white (and a lower proportion black and Hispanic) than individuals in control worksites. To address imbalance on some observable characteristics, we followed two common strategies. First, we weighted the treatment and control groups to be more balanced on observed characteristics (such that each group mirrors the overall employee population). Second, we include observable characteristics as covariates in the regression analyses below. Neither of these strategies, however, guarantees that there are no idiosyncratic differences in unobserved confounders.

The sample weights that we generate to address the imbalance on some demographics were constructed to balance treatment and control samples on age, sex, and race while minimizing variance of the weights for a given level of balance. A given level of balance is defined as the tolerance of a certain magnitude of difference in the standardized means between treatment and control. The tradeoff for more precise balance is a larger variance in the weights. In our base analysis, we will use weights that tolerate a difference in the standardized means in age, sex, and race up to 0.001 standard deviations between treatment and control. In sensitivity analyses, we will loosen the tolerance in constructing these weights to 0.01 standard deviations between treatment and control. The balance weights are calibrated to match the characteristics of the overall study population. This method has been shown to perform better than a model-based approach that fits a propensity score.⁹ Once we deploy the sample balance weights, all demographic characteristics are balanced. Job characteristics, including prevalence of Cigna insurance, are balanced in all analytical subsamples.

Table 9 examines individual-level characteristics collapsed to the worksite level, as well as county-level characteristics, using 2015 data from the U.S. Census Bureau. This suggests that the employee pools at the worksites roughly reflect the characteristics of the local population. The fact that treatment and control groups were located in idiosyncratically different parts of the country can be appreciated from **Figure 1**, where, for example, worksites in Ohio and Virginia were disproportionately randomly assigned to treatment and worksites in Florida were more likely to be randomly assigned to control.

VI. Statistical Analyses

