The key identifying assumption is that the only mechanism through which being employed in a treatment worksite affects outcomes is through the availability of the wellness program. There are two threats to this assumption. First, to the extent that covariates were not balanced at baseline and those covariates affect the outcomes of interest, that imbalance could bias our estimates. We control for observed covariates and apply weights to balance covariates between treatment and control. Despite these adjustments, unobserved covariates might still be imbalanced.

Second, to the extent that the wellness program affected hiring or tenure of employees, their presence in the data set may be endogenously determined. We address the issue of endogenous entry by pre-specifying a subsample of those who were already employed at the time the intervention began. We defined this more restrictive “stable employment” subsample as comprising employees who had worked continuously for 13 weeks prior to the wellness program. This comes at a cost of reducing the overall sample size. Our goal in choosing the definition for this subsample was to balance the costs and benefits, as detailed in Appendix 2.

In this stably employed subsample, however, exit from the firm's workforce is still potentially endogenous. We deal with this concern in two ways. First, we will test balance on exit between treatment worksites vs. from control worksites overall and for subgroups. Indeed, tenure and time worked are among our primary outcomes. To the extent that we observe any unbalanced exit, we will perform a bounding exercise (assuming that those who exited have outcomes working against any observed effects of the intervention).

D. Subgroup analyses

We pre-specified three subgroup analyses. We selected these subgroups based on differences in key outcomes within the control group for those with different baseline characteristics, such as differences in medical spending by age or in reported exercise by sex (**Table 11**).

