Notes: Employees are included if they answered at least 1 question on the PHA. Demographic characteristics are plausibly unaffected by the treatment. Demographics are taken from the Team Member database supplied by BJ's and based on the first entry for an individual during the treatment period. Age is defined as of December, 2014 (pre-treatment). Column 1 reports the means for employees in the treatment group while column 2 reports the means for the primary control employees. Treatment status is defined by the first worksite an employee appears in during the treatment period. Column 3 reports the p-value for the comparison between the employees at treatment worksites and the employees at primary control worksites. All regressions are weighted by a weight that balances treatment and control on demographic characteristics and cluster standard errors by worksite.

Panel C: Cigna Insured Subsample

	(1) Treatment (n=1385)	(2) Primary Control (n=1354)	(3) Primary + Secondary Control (n=7174)	(4) (1) vs (2) P value	(5) (1) vs (3) P value
Demographics					
Age (yrs)	42.7	42.1	42.6	0.321	0.836
Female (%)	44.4	43.8	44.6	0.768	0.949
Race (%)				0.996	>0.999
Black	16.9	14.9	17.7		
White	62.7	66.6	61.2		
Hispanic	14.7	14.9	15.9		
Other	5.6	3.7	5.2		

Notes: Employees are included if they had at least 1 month of Cigna health insurance coverage. Demographic characteristics are plausibly unaffected by the treatment. Demographics are taken from the Team Member database supplied by BJ's and based on the first entry for an individual during the treatment period. Age is defined as of December, 2014 (pre-treatment). Column 1 reports the means for employees in the treatment group while columns 2 and 3 report the means for the primary control employees and all control employees (primary and secondary), respectively. Treatment status is defined by the first worksite an employee appears in during the treatment period. Column 4 reports the p-value for the comparison between the employees at treatment worksites and the employees at primary control worksites and column 5 reports the p-value for the comparison between the employees at treatment worksites and all employees at control worksites. All regressions are weighted by a weight that balances treatment and control on demographic characteristics and cluster standard errors by worksite.

Panel D: Stably Employed Subsample

	(1)	(2)	(3)	(4)	(5)

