Note: Control means and first stage estimates of the impact of TREATMENT on alternate definitions of PARTICIPATION. All regressions include demographic and employment controls (age, sex, age-sex interactions, race/ethnicity, full-time status, paid hourly status, and job category) and cluster standard errors at the worksite level. All samples other than the sample with Cigna coverage also include a control for whether or not the employee ever had Cigna coverage during the treatment period. Employee-level regressions are weighted by a weight that balances treatment and control on demographic characteristics. Standard errors shown in parenthesis and p-values in brackets.

Panel B: Employee-level—Stably Employed Sub-sample

	All		Surveyed		Cigna	
	(7) Control Mean	(8) Estimated First Stage	(9) Control Mean	(10) Estimated First Stage	(11) Control Means	(12) Estimated First Stage
Completed any module (%)	0.57	49.75 (2.82) [0.00]	3.90	79.22 (2.74) [0.00]	0.97	59.54 (3.24) [0.00]
Modules completed (#)	0.02	2.56 (0.21) [0.00]	0.15	5.41 (0.39) [0.00]	0.04	3.41 (0.29) [0.00]
3 or more modules (%)	0.35	35.04 (2.47) [0.00]	2.96	67.78 (3.39) [0.00]	0.61	45.79 (3.15) [0.00]
Average total incentive payment (\$)	0.75	97.62 (8.45) [0.00]	5.92	217.91 (15.74) [0.00]	1.54	163.36 (13.80) [0.00]
N	13,000	15,344	747	1,396	5,779	6,907

Note: Control means and first stage estimates of the impact of TREATMENT on alternate definitions of PARTICIPATION. All regressions include demographic and employment controls (age, sex, age-sex interactions, race/ethnicity, full-time status, paid hourly status, and job category) and cluster standard errors at the worksite level. All samples other than the sample with Cigna coverage also include a control for whether or not the employee ever had Cigna coverage during the treatment period. Employee-level regressions are weighted by a weight that balances treatment and control on demographic characteristics. Standard errors shown in parentheses and p-values in brackets.

Panel C: Worksite level

	All		Surveyed		Cigna	
	(1) Control Mean	(2) Estimated First Stage	(3) Control Mean	(4) Estimated First Stage	(5) Control Means	(6) Estimated First Stage
Completed any module (%)	0.22	28.19 (1.27) [0.00]	3.07	62.25 (1.89) [0.00]	0.91	57.29 (2.83) [0.00]
Modules completed (#)	0.01	1.17 (0.09) [0.00]	0.11	3.49 (0.22) [0.00]	0.03	3.18 (0.27) [0.00]
3 or more modules (%)	0.12	16.69 (1.12) [0.00]	2.27	46.65 (2.16) [0.00]	0.54	43.68 (2.76) [0.00]

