- **Summary:** These two seven-week programs were exercise-based. Employees were supposed to complete 20 minutes or more of cardiovascular exercise at least 3 days per week and track their activity in an exercise log.
- **Incentive:** Employees who completed 6 of the 7 weeks in either round 1 or round 2 earned a \$25 BJ's gift card. Employees who completed 12 out of 14 weeks over both rounds were eligible to enter a raffle at their worksite for a Fitbit. Employees with Cigna coverage who completed 12 out of 14 weeks received a \$150 fitness reimbursement from Cigna on top of the raffle entry and gift card. Worksites were also in competition with the

top worksite based on % participation and the top worksite with the highest average weekly minutes of exercise reported each receiving a trophy to display in the worksite, winner buttons for employee lanyards, and bragging rights.

Module 5

Maintain Don't Gain (11/23/2015-12/20/2015)

- Summary: This four-week challenge helped employees track their weight each week and offered tips on how to add physical activity to a daily routine and substitutions for options with fewer calories when dining out.
- Incentive: Employees who completed at least 3 out of the 4 weeks of weight tracking and returned the verification form received a \$25 BJ's gift card.

Module 6

Power Down the Pressure (1/18/2016-2/19/2016)

- Summary: This four-week program encouraged employees to learn effective methods for managing stress by asking them to complete at least one activity from a list of options for the week for at least 3 days of the week. Week 1 was called "Unplug" and included activities such as refraining from watching TV for a day or having an electronic-free meal with family or friends. Week 2 was titled "Boost Your Mood" and included activities like doing a random act of kindness, getting 8 hours of sleep, or spending time with a friend. Week 3 was "Exercise" and asked employees to take a new exercise class or do a 30-minute workout/activity outdoors. The final week was called "Relaxation and Meditation" and encouraged employees to keep a stress journal, color, and meditate.
- Incentive: Employees who completed all four weeks of the program by completing at least 3 days of stress management activities a week and returned the verification form received a \$25 BJ's gift card.

Module 7

Weight Loss Boot Camp (3/14/2016-4/8/2016)

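### The stably employed rule fixes employment before the program but not Cigna cover, so the claims outcomes in Table 4 are not protected against selection into cover after randomization; no such selection is shown, and the check is cheap

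*Combined protocol and SAP*

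**What the plan says.** Section IV.A2 states that claims are available "only for the roughly 37% of employees who were enrolled in a BJ's employer-sponsored Cigna health insurance plan at any given time". It drops claims dated before the start of Cigna eligibility or more than 30 days after enrollment ends, and it annualizes partial-year enrollees. The plan therefore expects people to gain and lose cover during follow-up.

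The notes to Table 8 Panel C give the rule for the claims sample: "Employees are included if they had at least 1 month of Cigna health insurance coverage". That sentence names no window. The nearest statement of one is the covariate note under Table 10, which refers to "whether or not the employee ever had Cigna coverage during the treatment period".

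Section V.A introduces the stably employed subsample (13 weeks of employment before the program) and says its members "thus cannot have entered because of the treatment". Section VI.C adds that exit from the firm's "workforce is still potentially endogenous", and plans a test of exit by arm and, if exit is unbalanced, a bounding exercise. Section V.B states: "Job characteristics, including prevalence of Cigna insurance, are balanced in all analytical subsamples".

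Appendix 1 describes rewards that depend on Cigna status. For Modules 3 and 4, "Employees with Cigna coverage who completed 12 out of 14 weeks received a" $150 reimbursement in addition to what other employees could earn. Similar $150 reimbursements appear in Module 2, Modules 10-11 and Module 12. Module 1 includes teaching on choosing a health plan.

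**The concern.** The plan treats treatment-driven entry as one of two main threats and answers it with the stably employed subsample. For absenteeism, reviews and tenure that answer works, because employment alone puts a person in the sample. For the seven outcomes of Table 4 a second condition applies: the person must hold Cigna cover. That condition is not fixed before randomization. A stably employed person who first takes Cigna cover in 2016 enters the claims sample then, and one who drops it while still employed stops being observed.

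If assignment changed who takes or keeps Cigna cover, Table 4 would mix a change in who is insured with a change in spending and use. This would also apply in the columns that a reader will take as the safe ones. Spending is among the plan's headline questions. No test or bound on enrollment during treatment is planned.

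**Working it through.** **1. Do the counts agree?** Table 8 Panel C gives 1,385 treatment and 7,174 control employees in the claims sample; 1,385 + 7,174 = 8,559, the Table 10 Panel A total. Table 8 Panel D gives 2,344 and 13,000 stably employed; the sum is 15,344, the Table 10 Panel B total. The stably employed claims sample is 6,907 in all with 5,779 controls (Table 10 Panel B; Table 4 has the same 5,779), so 6,907 - 5,779 = 1,128 are treated.

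**2. Share of each arm in the claims sample (raw counts).**

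| Sample | Treatment | Control | Gap |
|---|---|---|---|
| Stably employed, v all controls | 1,128/2,344 = 48.1% | 5,779/13,000 = 44.5% | 3.7 points |
| All employees, v all controls | 1,385/7,288 = 19.0% | 7,174/41,376 = 17.3% | 1.7 points |
| All employees, v primary controls | 1,385/7,288 = 19.0% | 1,354/7,377 = 18.4% | 0.6 points |

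The documents do not give the stably employed claims count for primary controls alone.

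**3. Could the 3.7 points be chance?** Pooled share 6,907/15,344 = 0.450. Unclustered SE = sqrt(0.450 × 0.550 × (1/2,344 + 1/13,000)) = 1.12 points, so z = 3.67/1.12 = 3.3. Worksites average 15,344/160 = 96 stably employed people. With design effect 1 + 95 × ICC (the ICC is not in the documents and is assumed):

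| ICC | Design effect | z | p |
|---|---|---|---|
| 0 | 1.0 | 3.3 | 0.001 |
| 0.01 | 1.95 | 2.35 | 0.019 |
| 0.02 | 2.9 | 1.9 | 0.054 |
| 0.05 | 5.75 | 1.4 | 0.17 |

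Significance at 5% is lost above an ICC of about 0.019. For all employees against primary controls, z is 1.0 even without clustering.

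**4. Could it be race mix?** The counts are unweighted, and Table 8 Panel A.1 shows a raw race imbalance (57.7% v 48.8% white, p < 0.001). As a rough check for all employees, divide the control race shares in Panel C by those in Panel A.2: white 61.2/50.1 = 1.22, black 17.7/25.9 = 0.68, Hispanic 15.9/17.2 = 0.92, other 5.2/6.8 = 0.76. Applying these to the raw race mix of each arm gives 1.034 for treatment and 0.995 for control, a ratio of 1.039. The expected treatment share is 17.34% × 1.039 = 18.0%. Race mix alone would thus explain about 0.7 of the 1.7 points. The same check cannot be made for the stably employed claims sample, whose race mix in treatment is not shown.

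**5. Could it predate the program?** Table 8 Panel D shows 2014 enrollment as 0.4 in every column, with p = 0.964 against primary controls and 0.244 against all controls. One decimal cannot exclude a gap of several points. p = 0.244 corresponds to z = 1.17. At a prevalence of 0.4 the unclustered SE is sqrt(0.24 × (1/2,344 + 1/13,000)) = 1.10 points, which implies a 2014 difference of about 1.3 points, or 1.8 at ICC 0.01 and 3.1 at ICC 0.05. Its direction is not given.

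**6. What the plan's balance evidence covers.** Panel D tests 2014 cover. Panel C tests age, sex and race among people already in the claims sample, and these are the variables the weights balance. Neither tests enrollment in 2015-2017, so the Section V.B statement does not settle the point.

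**The case against.** The strongest reply is that nothing in the documents shows the program moved anyone into or out of Cigna cover. Most of that reply stands.

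- A reader might infer from 48.1% v 44.5% that the program drew people into cover. Steps 3 to 5 give three other explanations, and against the primary controls the all-employee gap is only 0.6 points. Nor does 48.1% set beside a 2014 figure of 0.4 show a rise caused by treatment: the 2014 figure is weighted and rounded, and it covers one year rather than three.
- A reader might infer that the program pays people to enroll. It does not. It offers members more for completing modules, and the first-stage incentive in the stably employed Cigna sample is $163 over three years (Table 10 Panel B), or about $54 a year. The documents also do not say whether Cigna members at control sites could claim these reimbursements by another route.
- A reader might turn the gap into a dollar bias by giving the 86 extra treated members (1,128 - 0.4445 × 2,344) a spending level taken from Table 11. The documents do not support this. They do not say who would enter. Equation (1) adjusts for age, full-time status, pay type and job type, which would remove much of any difference along those lines. The whole gap would also have to be induced.
- The Section V.A sentence is true of employment, which is its subject. The problem lies in carrying it over to Table 4.

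What the reply does not remove is the structural point: cover can change after randomization, and no planned test or bound addresses it.

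**Conclusion.** The concern holds as a gap in protection, not as a demonstrated error. The stably employed columns of Table 4 are protected against treatment-driven entry to employment, but not against treatment-driven gain or loss of Cigna cover. The size of any resulting bias is unknown and may be zero. The raw gap of 3.7 points does not measure it: part or all of the gap may be chance, race mix or a prior difference. Equally, a small net gap would not exclude a change in which people are covered.

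This rests on one reading: that the one-month rule in Table 8 Panel C uses the window in the Table 10 covariate note (any time in the treatment period). The claims-date rules in Section IV.A2 fit that reading. The ICCs are assumptions.

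**What to change.** 1. Among all stably employed employees, estimate the effect of assignment on any Cigna cover and on months of cover in 2015-2017, with the plan's weights and worksite clustering.
2. Add to Table 4 a pre-specified sensitivity analysis restricted to stably employed employees enrolled in Cigna before January 2015, using the 2014 enrollment data already held for Table 8 Panel D. Keep the current sample as the base analysis.
3. Extend the Section VI.C exit test and bounding to gain or loss of Cigna cover while still employed.
4. State in Section V.A that protection from endogenous entry applies to employment and not to entry into the claims sample.

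The cost is SAP wording and a few more runs on data already held. The sensitivity cohort is less precise. At a 2014 share of 0.40 it has about 938 treated and 5,200 control employees, if all of them kept cover into 2015. With the Table 4 SD of 19,056.92, the unclustered SE for medical spending goes from 19,056.92 × sqrt(1/1,128 + 1/5,779) = $620 to 19,056.92 × sqrt(1/938 + 1/5,200) = $676, about 9% larger. Across the rounding of 0.4 (0.45 to 0.35) it is $637 to $723, or 3 to 17% larger. That loss is a reason to make this cohort a sensitivity analysis and not a replacement.
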